We hypothesize that early improvement in small airway function may be a significant contributor to the therapeutic response of anti-IL-5 monoclonal antibody therapy in patients with severe uncontrolled eosinophilic asthma. We speculate that SAD could be effectively evaluated using IOS. Consequently, this study could lead to novel SAD subtypes with possible clinical relevance in the context of treatment with anti-IL-5 factor. We hypothesize that healthy individuals and patients with severe controlled asthma would disclose a lesser extent of SAD than patients with severe uncontrolled eosinophilic asthma with or without fixed airway obstruction.

OBJECTIVES

We sought to describe early changes in respiratory mechanics by means of IOS in patients with severe eosinophilic asthma commencing mepolizumab treatment. The detected parameters will be compared to a group of matched for age and gender healthy controls as well as with a group of patients with severe controlled asthma matched for age and gender requiring high dose inhaled corticosteroids (ICS) /long-acting beta-agonist (LABA) combination therapy to prevent asthma from becoming uncontrolled.

METHODS

Study Population

Our sample will consist of 40 patients between 18 and 82 years of age with uncontrolled severe eosinophilic asthma despite receiving high dose ICS/LABA combination therapy.

Principal inclusion criteria:

- Written informed consent
- Male or female outpatient aged 18 to 82 years inclusive
- History of bronchial asthma for at least six months as defined by ATS criteria [26].

The patients will be required to have one or more of the following objective physiological criteria: positive results on methacholine or mannitol challenge during the previous year, bronchodilator reversibility to 400 mg of inhaled Salbutamol of $FEV_1 \geq 12\%$ and 200ml or peak flow variability of $\geq 20\%$ over two weeks.

- Diagnosis of severe asthma, defined as asthma that requires treatment with high dose inhaled corticosteroids plus a second controller and/or systemic corticosteroids to prevent it from becoming uncontrolled or that remains uncontrolled despite this therapy [27, 28].

All patients will be medicated with at least 880 μg of fluticasone propionate or the equivalent by inhalation per day and at least three months of treatment with an additional controller. Patients will be allowed to continue their anti-asthma therapy throughout the study.

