- Patients should have uncontrolled asthma commencing mepolizumab treatment, based on investigator assessment, including one or both of the following:

- Poor symptom control (frequent symptoms or reliever use, activity limited by asthma, night waking due to asthma), defined as ACQ consistently ≥ 1.5 or ACT <20 .
- Frequent exacerbations (≥ 2 /year) requiring oral corticosteroids, or severe exacerbations (≥ 1 /year) requiring hospitalization or burst of systemic corticosteroids (≥ 3 days) [29].
- All patients will have an eosinophil count of at least 150 cells per microliter in the peripheral blood at screening or at least 300 cells per microliter at some time during the previous year.

Control groups

Control groups will be a set of 50 healthy individuals matched for age and gender and 40 patients with severe well-controlled asthma requiring high dose ICS/LABA combination therapy from becoming uncontrolled, as previously defined, matched for age and gender.

Principal exclusion criteria:

- Diseases and health status:
 - clinically relevant abnormal laboratory values suggesting an unknown disease and requiring further clinical evaluation
 - suffering from COPD (i.e., chronic bronchitis or emphysema) and/or other relevant lung diseases causing alternating impairment in lung function
- Asthmatic patients and healthy controls currently smoking or with a smoking pack history greater than 10 will be excluded.

Common exclusion criteria:

- pregnancy
- intention to become pregnant during the course of the study
- breast feeding
- participation in another study within the 30 days preceding and during the present study
- known or suspected non-compliance, alcohol or drug abuse
- inability to follow the procedures of the study, e.g., due to language problems, psychological disorders

Sampling

Approximately 1000 patients with asthma per year are treated in the external Unit of Asthma of Respiratory Medicine Department of the University of Thessaly in

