Greece. Nevertheless, in order to certainly achieve the estimated study sample size, to maximize the response rate and to reduce survey error, the Respiratory Medicine Department of the University of Thessaly will cooperate with a network of private respiratory physicians in Central and Northern Greece that serves a population base of about 3,000,000. Asthma education programs will regularly take place to raise severe asthma awareness, improve asthma control and management by creating a community Interlink between Respiratory Medicine Department and private sector from across central and northern Greece.

Furthermore, Respiratory Medicine Department of the University of Thessaly, via more than 12 clinical-community partnership spirometry surveillance programs with ten primary Health Care Centers in Central and Northern Greece, has already created a network of researchers, experts, and healthcare practitioners which is vitally important to early identify patients with uncontrolled asthma.

Ethics

Verbal and written informed consent will be obtained from all subjects before the study, according to the Helsinki declaration [30]. The protocol has already been approved by the Larissa University Hospital Ethics Committee (Approval number: 48841/25/10/2019)

Target enrolment/sample size: (Required for clinical studies)

130 (40 patients with severe uncontrolled eosinophilic asthma commencing mepolizumab treatment, 40 patients with severe controlled asthma medicating with high dose ICS/LABA combination therapy, and 50 healthy individuals matched for age and gender)

Anticipated rate of enrolment: (Required for clinical studies)

1 to 4 patients per month

Estimated study start date: (FSFV/Study Start/Analysis Start)

May 2020

Estimated study completion date: (LSLV/Study End/Analysis Complete)

September 2023

Study Design and Methods

This will be a 2-year prospective, cohort study. Patients will receive mepolizumab, which will be administered as a 100-mg subcutaneous dose every four weeks. Subjects

will be present for subcutaneous mepolizumab (100 mg) injection initially at visit 0 (Week 0), then for reassessment at two (Week 2) and four weeks (Week 4) and continued monthly treatment with reassessment at three (Week 12) and six months (Week 26). The patients will not alter their usual treatment regimen between Week 0 and Week 12; thus mitigating any other potential confounder.

Period	Enrollment	Follow-up		
Visit		0	2	4
Week	0 - 72			12

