5) To investigate the association between the changes in respiratory mechanics by means of IOS and the quality of life measurement as defined by AQLQ in patients with severe eosinophilic asthma before and after mepolizumab treatment.

Statistical Plan or Data analysis

Data will be analyzed using the statistical program SPSS 22 (IBM Corporation, Armonk, NY, USA). Quantitative variables will be presented as mean with standard deviation (SD), and qualitative variables will be presented as frequencies with percentages. Chi-square test will be used to explore any associations between qualitative variables. To identify differences between two independent groups when the dependent variable will either ordinal or continuous, unpaired t-tests or Mann–Whitney U tests will be used for normally distributed and skewed data, respectively. Differences between more than two unrelated groups will be tested by one-way analysis of variance (ANOVA). A result will be considered statistically significant when the P-value will be <0.05 .

Limitations

This will be the first study to investigate small airway dysfunction using IOS in patients with severe uncontrolled eosinophilic asthma commencing mepolizumab treatment. While oscillometry measurements are portrayed as a marker of small airway dysfunction, the normal reference ranges or threshold to define SAD has not been established yet. However, IOS has many advantages as is the most commonly used type of FOT in clinical practice including the use of simple tidal breathing maneuvers against forced maneuvers applied in spirometry and thus require less effort, while it demonstrates a change in early disease wherein spirometry is normal [16].

What is your planned publication? Abstract, Manuscript, Study report

- Planned Publication date (Abstract):
January 2022
- Planned Publication date (Manuscript):

March 2022

- Planned Publication Date (Study report):

March 2020

Planned Publication Date (Study report)	Planned Publication date (Abstract)	Planned Publication date (Manuscript)
March 2020	January 2022	March 2022

References

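### The control groups are matched on age and gender, but the listed between-group tests use neither; adding both as covariates is a cheap gain in precision, mainly for secondary endpoint 2

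*Combined protocol and SAP*

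**What the plan says.** **Design.** The Objectives state: "The detected parameters will be compared to a group of matched for age and gender healthy controls", and also to patients with severe controlled asthma, again matched on age and gender. The Control groups section gives the sizes: "Control groups will be a set of 50 healthy individuals matched for age and gender and 40 patients with severe well-controlled asthma". The target enrolment entry repeats the matching. The inclusion criteria admit a wide age span: "Male or female outpatient aged 18 to 82 years inclusive".

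**Endpoints.** Secondary endpoint 1 compares IOS in uncontrolled patients before therapy with healthy individuals. Secondary endpoint 2 compares patients starting anti-IL-5 treatment with controlled severe asthma.

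**Analysis.** Under Statistical Plan or Data analysis, the two-group rule is "To identify differences between two independent groups when the dependent variable will either ordinal or continuous, unpaired t-tests" or Mann-Whitney U tests, which "will be used for normally distributed and skewed data, respectively". For three groups: "Differences between more than two unrelated groups will be tested by one-way analysis of variance (ANOVA"). No covariate, pair, stratum or regression is named.

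**Silent points.**
- The plan does not assign a test to any endpoint.
- It does not say whether matching is individual or by frequency, or how close it must be.
- It gives no SD for any IOS index and no share of IOS variance due to age or gender.
- The IOS section states no percent-predicted or z-score form for R5, R20, R5-R20, X5, Fres or AX. The Spirometry section does use percent-predicted values.

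**The concern.** Matching removes age and gender from the difference between group means, but an unadjusted test leaves their contribution in the standard error. If the two factors predict IOS, the standard error is then too large for the design, the test rejects too rarely under the null, and a moderate true difference is easier to miss. If the matching is loose, whatever imbalance remains goes straight into the unadjusted difference.

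The comparisons at stake are the reason for recruiting 50 + 40 = 90 of the 130 participants. With no stated percent-predicted form for IOS, nothing in the plan accounts for age and gender indirectly.

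**Working it through.** **Step 1: the plan's own figure.** 40 + 40 + 50 = 130, which agrees with the target enrolment. No effect size, SD or power is given, so there is no sample size calculation to reproduce.

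**Step 2: inputs.** From the documents: group sizes, age range 18 to 82, significance at 0.05. Assumed: two-sided tests; R² of 0, 10, 20 or 30%; age uniform; gender 50:50; three quarters of R² from age and one quarter from gender.

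**Step 3: formula, equal variances, close balance.** In SD units the unadjusted SE is √(1/n₁ + 1/n₂) and the adjusted SE is that times √(1 − R²). The smallest difference detectable with 80% power is (1.960 + 0.842) × SE.

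- 40 vs 40: SE = 0.2236. Detectable difference 0.626 unadjusted; 0.594, 0.560 and 0.524 adjusted at R² 10, 20 and 30%.
- 40 vs 50: SE = 0.2121. Detectable difference 0.594 unadjusted; 0.564, 0.532 and 0.497 adjusted.

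**Step 4: simulation for endpoint 2.** 40 vs 40, 40,000 runs per cell, controls of the same gender and within 3 years, linear model with HC3 standard errors.

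| R² | 0% | 10% | 20% | 30% |
|---|---|---|---|---|
| Power at 0.5 SD, unpaired t | 60% | 60% | 61% | 61% |
| Power at 0.5 SD, adjusted | 58% | 62% | 68% | 73% |
| Adjusted CI width as share of unadjusted | 103% | 97% | 92% | 86% |
| Power at 0.8 SD, unpaired t | 94.1% | 95.1% | 96.2% | 96.9% |
| Power at 0.8 SD, adjusted | 93.5% | 95.7% | 97.5% | 98.6% |

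**Step 5: type I error, 40 vs 50, equal variances.**

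- Unpaired t, matched within 3 years: 5.1, 3.9, 2.8 and 2.2% at R² 0, 10, 20 and 30%.
- Unpaired t, matched within 15 years (12,000 runs): 5.2, 3.9, 3.0 and 2.4%.
- Unpaired t, no balancing: about 5%, so the conservatism goes.
- Adjusted model: 4.3 to 4.6%.

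**Step 6: endpoint 1, 40 vs 50.** With equal variances, power at 0.5 SD is 64, 65, 66 and 67% unadjusted and 63, 67, 72 and 78% adjusted, a gain like that for endpoint 2. Severe patients may well be more variable than healthy people. Taking the patient residual SD as a multiple of the healthy SD (assumed; 4,000 runs per cell), the change in power is:

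| R² | 0% | 10% | 20% | 30% |
|---|---|---|---|---|
| Adjusted HC3 minus Welch, SD ratio 2 | -1 | 0 | +2 | +5 |
| Adjusted HC3 minus Welch, SD ratio 3 | -1 | 0 | +1 | +2 |
| Rank model minus Mann-Whitney, SD ratio 2 | -4 | -2 | 0 | +2 |
| Rank model minus Mann-Whitney, SD ratio 3 | -5 | -4 | -2 | -1 |

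Simulation error is up to √(0.25/4000) = 0.8 points on each single power. At R² 10 to 30% the HC3 interval is 94 to 100% as wide as Welch's. Type I error is 4.6 to 5.0% with HC3 but 6.6 to 7.8% for the ordinary linear model, so the robust errors are needed.

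**Step 7: skewed index.** Log-normal errors (sigma 0.7, assumed), 40 vs 40, 0.5 SD, 20,000 runs. Power at R² 0, 10, 20 and 30%:

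- Mann-Whitney: 91, 86, 80 and 77%.
- Rank model with HC3: 90, 89, 89 and 90%.
- Raw-scale linear model with HC3: 62, 67, 70 and 75%.

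The raw-scale model should therefore not replace Mann-Whitney for a clearly skewed index.

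**The case against.** The strongest reply is that nothing is broken. The design deals with age and gender by matching, the tests are valid in that respect, and only secondary endpoints are involved. No passage says that age or gender predicts IOS. At R² 0 adjustment costs about 2 points, at 10% it gains about 2, and only an assumed 20 to 30% combined with a moderate difference gives 7 to 12. This stands, and it is why the point is an improvement and not a correction.

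Endpoint 1 is weaker still. Its variances may differ, and its difference may be large: the Scientific Rationale cites a small-airway share of resistance of 24% in healthy adults and 51% in severe asthma, with no SD. This also stands.

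Conservatism might be welcome, since six IOS indices in two contrasts make 12 tests at 0.05 with no multiplicity control. True, but protection of unknown size is not a multiplicity plan.

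A reader might infer more than the documents support:

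- *The planned tests are invalid or biased because they ignore the matching.* Under balance they err on the cautious side, and without balancing the unpaired t holds about 5% with equal variances. With unequal variances a pooled t can reach 7.4%, but the plan says unpaired and does not say pooled, and that is a separate matter from matching.
- *A paired test is required.* Matching may be by frequency, and 40 vs 50 rules out plain one-to-one pairing with the healthy group.
- *IOS is certainly analysed on the raw scale.* The plan is silent and refers to cited sources for how the indices are derived.

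**Conclusion.** The point holds as a low-severity, nearly free improvement to secondary endpoints 1 and 2. The primary within-patient endpoint is not affected. The size depends on R², which the documents do not give.

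The case is best for endpoint 2, which compares two severe-asthma groups of equal size: from a loss of about 2 points to a gain of about 12 in power at 0.5 SD, and intervals 3% wider to 14% narrower, over R² 0 to 30%. This rests on equal variances and close matching. A reader might carry the same gain over to endpoint 1. That is supported only if healthy controls and patients are about equally variable; otherwise the change is about -1 to +5 points against Welch's test, and a rank model offers little or nothing over Mann-Whitney.

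Two links are inferred: that the generic two-group tests are meant for these endpoints, and that endpoint 2 is a baseline contrast, since its patients are described as starting treatment.

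**What to change.** For the two baseline contrasts (uncontrolled vs healthy, uncontrolled vs controlled), specify as the main analysis of each IOS index a linear model on group, age and gender with HC3 standard errors. Report adjusted differences with 95% CIs. Keep the unadjusted t or Mann-Whitney tests as supportive.

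For clearly skewed indices, keep Mann-Whitney as the planned test and report the age- and gender-adjusted difference with a bootstrap CI as supportive. Name those indices before the groups are compared. A log transformation may not be available, because R5-R20 is a difference and X5 a reactance. At R² 30% with equal spread this gives up the rank model's 13 points (90 against 77%). In return, the plan avoids a main test on ranks beside an interval on another scale, and a gain that largely disappears when spreads differ.

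**Cost.** SAP wording only: age and gender are the matching factors, so they are known for every participant. The model uses two degrees of freedom, loses about 1 to 2 points of power if R² is 0, and assumes linearity and common slopes across groups. The plan says "Data will be analyzed using the statistical program SPSS 22"; confirm that this version produces HC3 and bootstrap intervals, or name another program. Planned completion was September 2023, so if the group data have already been analysed, label the adjusted analysis post hoc.
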